### **4.2.2 Evaluation of target lesions**

This section provides the definitions of the criteria used to determine objective tumor visit response for TL.

**Table 10 - Evaluation of target lesions**

Complete Response (CR)	Disappearance of all target lesions since baseline. Any pathological lymph nodes selected as target lesions must have a reduction in short axis to <10 mm.
Partial response (PR)	At least a 30% decrease in the sum of the diameters of TL, taking as reference the baseline sum of diameters
Stable disease (SD)	Neither sufficient shrinkage to qualify for PR nor sufficient increase to qualify for progressive disease (PD)
Progressive disease (PD)	At least a 20% increase in the sum of diameters of target lesions, taking as reference the smallest sum on study (this includes the baseline sum if that is the smallest on study). In addition to the relative increase of 20%, the sum must also demonstrate an absolute increase of at least 5 mm
Not evaluable (NE)	Only relevant if any of the target lesions were not assessed or not evaluable or had a lesion intervention at this visit. Note: If the sum of diameters meets the PD criteria, PD overrides not evaluable as a target lesion response

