## **5 WITHDRAWAL OF PATIENTS**

### **5.1 CRITERIA FOR WITHDRAWAL**

Patients may be withdrawn from the NIS at any time. Specific reasons for withdrawing a patient from this NIS are:

1. Voluntary withdrawal by the patient who is at any time free to withdraw his/her participation in the NIS, without prejudice to further treatment (not applicable for retrospective patients).
2. Incorrect enrollment (inclusion/exclusion criteria are not fulfilled).
3. Inclusion in a clinical trial at any time during the study (not applicable for retrospective patients).

Discontinuation of the patient treatment is not a criterion for withdrawal from the study. In this case, the patient can continue in the study, until death, loss to follow-up, or end of study.

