### **2 Definition of measurable, non-Measurable, target and non-target lesions**

Only patients with measurable disease at baseline should be included in the study. Measurable disease is defined by the presence of at least 1 measurable lesion which has not been previously irradiated.

**Measurable:** A lesion, not previously irradiated, that can be accurately measured at baseline as  $\geq 10$  mm in the longest diameter (except lymph nodes which must have short axis  $\geq 15$  mm) with computed tomography (CT) or magnetic resonance imaging (MRI) and which is suitable for accurate repeated measurements.

**Non-measurable:** All other lesions, including small lesions (longest diameter  $< 10$  mm or pathological lymph nodes with  $\geq 10$  to  $< 15$  mm short axis at baseline\*).

Truly non-measurable lesions include the following: bone lesions, leptomeningeal disease, ascites, pleural/pericardial effusion, inflammatory breast disease, lymphangitic involvement of skin or lung, abdominal masses/abdominal organomegaly identified by physical examination that is not measurable by CT or MRI.

Previously irradiated lesions\*\*

Skin lesions assessed by clinical examination Brain metastasis

\* Nodes with  $< 10$  mm short axis are considered non-pathological and should not be recorded or followed as non-target lesions (NTL).

\*\*Localized post-radiation changes which affect lesion sizes may occur. Therefore, lesions that have been previously irradiated will not be considered measurable and must be selected as NTL at baseline and followed up as part of the NTL assessment.

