## **4.2 Target lesions**

### **4.2.1 Documentation of target lesions**

A maximum of 5 measurable lesions, with a maximum of 2 lesions per organ (including lymph nodes), representative of all lesions involved should be identified as TL at baseline. Target lesions should be selected on the basis of their size (longest diameter for non-nodal lesions or short axis for nodal lesions), but in addition should be those that lend themselves to reproducible repeated measurements. It may be the case that, on occasion, the largest lesion does not lend itself to reproducible measurement in which circumstance the next largest lesion, which can be measured reproducibly, should be selected.

The site and location of each TL should be documented as well as the longest diameter for non-nodal lesions (or short axis for lymph nodes). All measurements should be recorded in millimeters. At baseline, the sum of the diameters for all TL will be calculated and reported as the baseline sum of diameters. At follow-up visits the sum of diameters for all TL will be calculated and reported as the follow-up sum of diameters.

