#### **Special cases:**

For TL measurable in 2 or 3 dimensions, always report the longest diameter. For pathological lymph nodes measurable in 2 or 3 dimensions, always report the short axis.

If the CT/MRI slice thickness used is >5mm, the minimum size of measurable disease at baseline should be twice the slice thickness of the baseline scan.

If a lesion has completely disappeared, the longest diameter should be recorded as 0 mm.

If a TL splits into 2 or more parts, then record the sum of the diameters of those parts.

If 2 or more TL merge, then the sum of the diameters of the combined lesion should be recorded for one of the lesions and 0 mm recorded for the other lesion(s).

If a TL cannot be measured accurately due to it being too large, provide an estimate of the size of the lesion.

When a TL has had any intervention eg, radiotherapy, embolization, surgery, during the study, the size of the TL should still be provided, where possible.

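### Table 10 makes a treated target lesion not evaluable only at the visit of the intervention, so shrinkage from local treatment can count as response later and lower the nadir

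*Protocol*

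**What the plan says.** Appendix C governs how response is derived.

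- **NE category (4.2.2, Table 10):** "Only relevant if any of the target lesions were not assessed or not evaluable or had a lesion intervention at this visit". The note to the row allows one override: "If the sum of diameters meets the PD criteria, PD overrides not evaluable as a target lesion response".
- **Treated lesions (4.2.1, special cases):** "When a TL has had any intervention eg, radiotherapy, embolization, surgery, during the study, the size of the TL should still be provided", so far as that is possible.
- **Vanished lesions (same list):** "If a lesion has completely disappeared, the longest diameter should be recorded as 0 mm", with no condition on why the lesion has gone.
- **Follow-up sum (4.2.1):** "At follow-up visits the sum of diameters for all TL will be calculated and reported as the follow-up sum of diameters". Treated lesions are not excepted.
- **Thresholds (Table 10):** partial response (PR) is a fall of at least 30% from the baseline sum, whatever the cause. Progression (PD) is a rise of at least 20% and at least 5 mm over the smallest sum on study.
- **Overall response (4.6, Table 12):** a target-lesion PR becomes an overall PR when non-target lesions have not progressed and there is no new lesion.

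Protocol section 13.3.1 lists ORR, DCR, time to response, duration of response and the waterfall plot under the primary criteria. PFS comes under 13.3.2.

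**The concern.** The NE clause looks like a safeguard: once a lesion has been cut out, embolized or irradiated, its size no longer shows what the drug did. The wording ties that safeguard to a single visit. Assessments follow routine practice, recommended at least every 6 months for prospective patients (section 3.1), and section 7.3 places no restriction on other treatment. A local procedure is therefore likely to fall between two assessments. At the next one the lesion is measured, or entered as 0 mm, and the smaller sum is compared with the untouched baseline sum.

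Two things are at stake. A patient can be classed as a responder with no drug effect, and each RET group has only 20 to 25 patients. The reduced sum also becomes the reference for PD, which carries through to duration of response and PFS.

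**Working it through.** **1. The plan's own figure.** Section 13.2 and Table 1 assume an ORR of 35% with SD 0.4770, which is √(0.35 × 0.65). The interval is 0.35 ± 1.96 × 0.4770/√n:

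- n = 20: 0.35 ± 0.209, or 14.1% to 55.9%
- n = 25: 0.35 ± 0.187, or 16.3% to 53.7%
- n = 30: 0.35 ± 0.171, or 17.9% to 52.1%

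All three match Table 1.

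**2. When local shrinkage reaches the PR threshold.** Let the treated lesion be a share *s* of the baseline sum, with the other target lesions unchanged. Removal changes the sum by −*s*, so PR needs *s* ≥ 30%. Halving changes it by −*s*/2, so PR needs *s* ≥ 60%. For equal-sized target lesions, up to the maximum of 5 (section 4.2.1):

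| Target lesions | One removed | Target-lesion response | One halved | Target-lesion response |
|---|---|---|---|---|
| 1 | −100% | CR | −50% | PR |
| 2 | −50% | PR | −25% | SD |
| 3 | −33.3% | PR | −16.7% | SD |
| 4 | −25% | SD | −12.5% | SD |
| 5 | −20% | SD | −10% | SD |

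Under Table 12 the overall response also needs no non-target progression and no new lesion. With a single target lesion removed, the overall response is CR if there are no non-target lesions or they have disappeared, and PR if they persist.

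**3. Effect on ORR.** One patient is 1/20 = 5 points or 1/25 = 4 points. The documents give no frequency, so the counts below are assumptions. The starting points are 7/20 and, as the nearest whole number to 35% of 25, 9/25. Intervals use p ± 1.96 × √(p(1 − p)/n).

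| Responses due to local treatment | n = 20 | n = 25 |
|---|---|---|
| 0 | 35.0% (14.1 to 55.9) | 36.0% (17.2 to 54.8) |
| 1 | 40.0% (18.5 to 61.5) | 40.0% (20.8 to 59.2) |
| 2 | 45.0% (23.2 to 66.8) | 44.0% (24.5 to 63.5) |

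**4. Effect on the nadir (illustrative sizes).** Take two target lesions of 20 mm, a baseline sum of 40 mm. One is excised, so the sum is 20 mm and becomes the smallest on study. The other grows to 25 mm: 25/20 is +25% and +5 mm, which meets PD. Without the excision, the same growth gives 45/40 = +12.5%, which is SD. The growth is real in both cases; the excision changes only how it is classified.

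**The case against.** The strongest reply is that the row can be read otherwise. Table 10 defines a visit response, so its last words may describe the state of the lesion when that visit is evaluated, and not the day of the procedure. On the narrow reading the clause would hardly ever apply. The request to keep reporting sizes has its own explanation, since the PD override needs a measured sum. An investigator could also call a treated lesion not evaluable at any later visit, and the SAP, not among the documents reviewed, may carry the flag forward. This shows that the text is ambiguous, but none of it requires NE at later visits. A rule that depends on each site's choice is weak for a primary criterion.

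Several limits stand. Eligibility requires unresectable disease (section 4.2, I 04), which makes complete removal less likely, although the appendix itself names surgery. With 4 or 5 equal lesions, or a lesion that is merely halved and is under 60% of the sum, PR is not reached. DCR is largely unaffected, because moving a patient from SD to PR generally leaves disease control unchanged.

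A reader might also infer two stronger points:

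- **That Appendix C contradicts itself**, because section 2 says "lesions that have been previously irradiated will not be considered measurable". That sentence governs the selection of lesions at baseline. It shows awareness that radiation alters size, but sets no rule for follow-up.
- **That treatment given off drug is credited to vandetanib**, because section 5.1 says "Discontinuation of the patient treatment is not a criterion for withdrawal from the study". Section 3.1 ends follow-up or data collection at objective progression or end of study, while 5.1, 6.1 and 7.2 continue to death, loss to follow-up or end of study. How to handle later systemic drugs is a separate estimand choice that the Table 10 wording does not settle.

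**Conclusion.** The point holds as a defect of wording. Taken literally, Table 10 and section 4.2.1 of Appendix C allow shrinkage from a local procedure to produce a CR or PR at later visits, and to reset the reference for PD. It needs a treated lesion of at least 30% of the baseline sum if removed or 60% if halved, other target lesions unchanged, no non-target progression and no new lesion. That an excised lesion is entered as 0 mm is inferred from the special cases, not stated for surgery.

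The size is 4 to 5 points of ORR per affected patient, against an interval half-width of about 19 to 21 points in Table 1. The number of affected patients is unknown. A reader might infer that the ORR will be seriously inflated; the documents give no frequency of local treatment and do not support that. This is a cheap correction to the derivation of a primary criterion and does not put the study's conclusions in doubt by itself.

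**What to change.** - In Table 10, make NE apply when a target lesion had an intervention *at or before this visit (any time since baseline)*. Keep the PD override.
- In section 4.2.1, state that sums including a treated target lesion are recorded but cannot support a new CR or PR, set the nadir, or enter the best percentage change. Responses documented before the intervention stand.
- In section 13.3, keep patients without an earlier response whose later assessments are NE in the ORR denominator as non-responders. That section leaves missing data out of percentages; if NE were treated as missing, these patients would drop out and ORR could rise.
- In the eCRF, record the date and type of each intervention by lesion. Section 8.2 lists treatment start and stop dates where available, but shows no lesion-level record.

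The cost is one sentence in each place, one eCRF field and a programming flag; a few assessments become NE. One trade-off should be accepted knowingly. After a large lesion is removed, PD by target lesions is harder to reach, because the sum must still exceed the earlier nadir by 20%: in the 40 mm example the remaining lesion would have to reach 1.2 × 40 = 48 mm. Progression by non-target or new lesions is unaffected. No patient's care changes.

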## 4.3 Non-target lesions

### 4.3.1 Evaluation of non-target lesions

All other lesions (or sites of disease) not recorded as TL should be identified as NTL at baseline. Measurements are not required for these lesions, but their status should be followed at subsequent visits. At each visit an overall assessment of the NTL response should be recorded by the Investigator. This section provides the definitions of the criteria used to determine and record overall response for NTL at the investigational site at each visit.

**Table 11 - Evaluation of non-target lesions**

Complete response (CR)	Disappearance of all non-target lesions since baseline. All lymph nodes must be non-pathological in size (< 10 mm short axis).
Non-CR/Non-PD	Persistence of 1 or more NTL
Progression (PD)	Unequivocal progression of existing non-target lesions. Unequivocal progression may be due to an important progression in 1 lesion only or in several lesions. In all cases the progression MUST be clinically significant for the physician to consider changing (or stopping) therapy.
Not evaluable (NE)	Only relevant when 1 or some of the non-target lesions were not assessed and, in the Investigator's opinion, they are not able to provide an evaluable overall non-target lesion assessment at this visit. Note: For patients without target lesions at baseline, this is relevant if any of the non-target lesions were not assessed at this visit and the progression criteria have not been met.

To achieve ‘unequivocal progression’ on the basis of NTL, there must be an overall level of substantial worsening in non-target disease such that, even in presence of stable disease or partial response in TL, the overall tumor burden has increased sufficiently to merit discontinuation of therapy. A modest ‘increase’ in the size of 1 or more NTL is usually not sufficient to qualify for unequivocal progression status.

#### 4.4 New lesions

Details of any new lesions will also be recorded with the date of assessment. The presence of 1 or more new lesions is assessed as progression.

A lesion identified at a follow-up assessment in an anatomical location that was not scanned at baseline is considered a new lesion and will indicate disease progression.

The finding of a new lesion should be unequivocal: ie, not attributable to differences in scanning technique, change in imaging modality, or findings thought to represent something other than tumor.

If a new lesion is equivocal, eg, because of its small size, the treatment and tumor assessments should be continued until the new lesion has been confirmed. If repeat scans confirm there is a new lesion, then the progression date should be declared using the date of the initial scan.

#### 4.5 Symptomatic deterioration

Symptomatic deterioration is not a descriptor of an objective response: it is a reason for stopping study therapy.

Patients with ‘symptomatic deterioration’ requiring discontinuation of treatment without objective evidence of disease progression at that time should continue to undergo tumor assessments where possible until objective disease progression is observed.

#### 4.6 Evaluation of Overall Visit Response

The overall visit response, as per RECIST 1.1, will be derived using the algorithm shown in [Table 12](#).

**Table 12 - Overall visit response**

Target lesions	Non-target lesions	New lesions	Overall response
CR	CR	No	CR
CR	NA	No	CR
NA	CR	No	CR
CR	Non CR/Non PD	No	PR
CR	NE	No	PR
PR	Non PD or NE	No	PR

Target lesions	Non-target lesions	New lesions	Overall response
SD	Non PD or NE	No	SD
NA	Non CR/Non PD	No	SD (Non CR/Non PD)
NE	Non PD or NE	No	NE
NA	NE	No	NE
PD	Any	Yes or No	PD
Any	PD	Yes or No	PD
Any	Any	Yes	PD

CR = Complete response, NA = Not applicable (only relevant if there were no NTLs at baseline), NE = Not evaluable, PD = Progressive disease, PR = Partial response, SD = Stable disease

## 5. Specifications for radiological imaging

These notes are recommendations for use in clinical studies. The use of standardized protocols for CT and MRI allows comparability both within and between different studies, irrespective of where the examination has been undertaken.

### 5.1 Computed tomography scan

Computed Tomography scans of the chest, abdomen, and pelvis should be contiguous throughout all the anatomic region of interest.

The most critical CT image acquisition parameters for optimal tumor evaluation using RECIST 1.1 are anatomic coverage, contrast administration, slice thickness, and reconstruction interval.

a. **Anatomic coverage:** Optimal anatomic coverage for most solid tumors is the chest, abdomen, and pelvis. Coverage should encompass all areas of known predilection for metastases in the disease under evaluation and should additionally investigate areas that may be involved based on signs and symptoms of individual patients. Because a lesion later identified in a body part not scanned at baseline would be considered as a new lesion representing disease progression, careful consideration should be given to the extent of imaging coverage at baseline and at subsequent follow-up time points. This will enable better consistency not only of tumor measurements but also identification of new disease.

b. **IV contrast administration:** Optimal visualization and measurement of metastases in solid tumors requires consistent administration (dose and rate) of intravenous contrast as well as timing of scanning. Typically, most abdominal imaging is performed during the portal venous phase and (optimally) about the same time frame after injection on each examination. An adequate volume of a suitable contrast agent should be given so that the metastases are demonstrated to best effect and a consistent method is used on subsequent examinations for any given patient. It is very important that the same technique be used at baseline and on follow-up examinations for a given patient. For patients who develop contraindications to contrast after baseline contrast CT is done, the decision as to whether non-contrast CT or MRI

(enhanced or non-enhanced) should be performed should also be based on the tumor type, anatomic location of the disease and should be optimized to allow for comparison to the prior studies, if possible. Each case should be discussed with the radiologist to determine if substitution of these other approaches is possible and, if not, the patient should be considered not evaluable from that point forward. Care must be taken in measurement of TL on a different modality and interpretation of non-target disease or new lesions, since the same lesion may appear to have a different size using a new modality. Oral contrast is recommended to help visualize and differentiate structures in the abdomen.

If iodine contrast media is medically contraindicated at baseline or at any time during the course of the study, then the recommended methods are: CT thoracic examination without contrast and abdominal and pelvis MRI with contrast. If MRI cannot be performed, then CT without intravenous contrast is an option for the thorax, abdomen and pelvis examination. For brain lesions assessment, MRI is the preferred method.

**c. Slice thickness and reconstruction interval:** It is recommended that CT scans be performed at 5mm contiguous slice thickness and this guideline presumes a minimum 5 mm thickness in recommendations for measurable lesion definition. Exceptionally, particular institutions may perform medically acceptable scans at slice thicknesses >5 mm. If this occurs, the minimum size of measurable lesions at baseline should be twice the slice thickness of the baseline scans.

All window settings should be included in the assessment, particularly in the thorax where lung and soft tissue windows should be considered. When measuring lesions, the TL should be measured on the same window setting for repeated examinations throughout the study. All images from each examination should be included in the assessment and not “selected” images of the apparent lesion.

## 5.2 Magnetic resonance imaging scan

Magnetic resonance imaging has excellent contrast, spatial and temporal resolution; however, there are many image acquisition variables involved in MRI, which greatly impacts image quality, lesion conspicuity and measurement. Furthermore, the availability of MRI is variable globally. The modality used at follow-up should be the same as was used at baseline and the lesions should be measured/assessed on the same pulse sequence. Generally, axial imaging of the abdomen and pelvis with T1 and T2 weighted imaging along with gadolinium-enhanced imaging should be performed. The field of view, matrix, number of excitations, phase encode steps, use of fat suppression and fast sequences should be optimized for the specific body part being imaged as well as the scanner utilized. It is beyond the scope appendix to prescribe specific MRI pulse sequence parameters for all scanners, body parts and diseases. Ideally, the same type of scanner should be used, and the image acquisition protocol should be followed as closely as possible to prior scans. Body scans should be performed with breath-hold scanning techniques if possible.

For these reasons, CT is the imaging modality of choice.

## **5.3 Fluorodeoxyglucose-positron emission tomography scans**

Fluorodeoxyglucose-positron emission tomography has gained acceptance as a valuable tool for detecting, staging and restaging several malignancies. If FDG-PET scans are included in a protocol, an FDG uptake period of 60 minutes prior to imaging has been decided as the most appropriate for imaging of patients with malignancy. Whole-body acquisition is important since this allows for sampling of all areas of interest and can assess if new lesions have appeared thus determining the possibility of interval progression of disease. Images from the base of the skull to the level of the mid-thigh should be obtained 60 minutes post injection. Positron-emission tomography camera specifications are variable and manufacturer specific, so every attempt should be made to use the same scanner, or the same model scanner, for serial scans on the same patient. Whole-body acquisitions can be performed in either 2- or 3-dimensional mode with attenuation correction, but the method chosen should be consistent across all patients and serial scans in the study.

